7.3. Informed Consent

Informed consent will be taken by the anaesthetist investigator when they see the participant prior to the surgery. The participant must personally sign and date the latest approved version of the Informed Consent form before any study specific procedures are performed. Written and verbal versions of the Participant Information and Informed Consent will be presented to the participants detailing no less than: the exact nature of the study; what it will involve for the participant; the implications and constraints of the protocol and any risks involved in taking part. It will be clearly stated that the participant is free to withdraw from the study at any time for any reason without prejudice to future care, without affecting their legal rights, and with no obligation to give the reason for withdrawal.

The participant will be allowed an hour to consider the information, and the opportunity to question the Investigator, or other independent parties to decide whether they will participate in the study. Written Informed Consent will then be obtained by means of participant dated signature and dated signature of the person who presented and obtained the Informed Consent. The person who obtained the consent must be suitably qualified and experienced, and have been authorised to do so by the Chief/Principal Investigator. A copy of the signed Informed Consent will be given to the participant. The original signed form will be retained at the study site.

7.4. Randomisation, blinding and code-breaking

Participants will not be randomised in this study. We are evaluating the performance of the LMA Protector airway device and thus if the participant signs the consent form the device will be used for their anaesthetic.

7.5. Assessments during Anaesthesia

The following measurements will be noted:

1. Assessment of the airway including Malampatti classification
2. The number of attempts at the insertion
3. Volume of air in cuff to achieve intracuff pressure of 60cmH₂O
4. Airway leak pressure
5. The ease of insertion
6. The time to first square capnography trace
7. Positive or negative bubble test

8. Lowest recorded oxygen saturation reading
9. Airway manipulations to establish airway
10. Complications during insertion
11. Complications intraoperatively
12. Complications during removal
13. Complications postoperatively

In addition to the above measurements the following aspects of the use of the device will be scored:

- 1) The quality of ventilation
- 2) The quality of the airway during maintenance
- 3) The ease of hands free anaesthesia
- 4) The overall usefulness of the device in the patient
- 5) The overall performance of the device

Lastly the investigators will note any complications during insertion, use and on removal of the device. Additionally, the participants will be asked about any post-operative oropharyngeal sequelae.

7.6. Subsequent Visits

First visit

During the first visit by the anaesthetist to the participant, at the anaesthetist's earliest opportunity, either in the recovery area or on the ward, the participants will be asked about the following complications, which will be graded as none, mild, moderate or severe).

- 1) Vomiting
- 2) Lip or tongue swelling
- 3) Hearing changes
- 4) Ear pain
- 5) Sore throat
- 6) Pain on swallowing
- 7) Jaw pain
- 8) Neck or mouth ache
- 9) Pain on speaking
- 10) Numbness of the tongue

Second visit (or telephone consultation)

During the second visit 24-48 hours post-operatively on the ward or via telephone the participants will be asked about the following complications, which will be graded as none, mild, moderate or severe).

- 1) Vomiting
- 2) Lip or tongue swelling
- 3) Hearing changes
- 4) Ear pain
- 5) Sore throat
- 6) Pain on swallowing
- 7) Jaw pain
- 8) Neck or mouth ache
- 9) Pain on speaking
- 10) Numbness of the tongue

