4. OBJECTIVES AND OUTCOME MEASURES

Objectives	Outcome Measures	Timepoint(s) of evaluation of this outcome

		measure (if applicable)
Primary Objective To assess the performance of the LMA Protector	1) First go insertion success rate, 2) First go successful ventilation rate, 3) Percentage of complication free insertions	At time of anaesthesia
Secondary Objectives To assess: 1) Time taken to achieve airway 2) Number of attempts to achieve patent airway 3) Complications during airway insertion 4) Complications during anaesthesia attributed to the airway 5) Complications during device removal 6) Complications after anaesthesia attributed to the airway 7) Quality of ventilation	1) Time to first square capnography waveform 2) Lowest oxygen saturation level 3) Monitor numbers of interventions needed to ensure airway patency 4) Monitor pre-defined complications occurrence during insertion of device, during anaesthesia, and on device removal 5) The quality of ventilation will depend on whether there was: a) adequate chest movement, b) tidal volume $> 7\text{ml/kg}$, c) stable SpO ₂ , and d) square capnography trace	At time of anaesthesia and post-operatively

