5. STUDY DESIGN

This is a prospective, multi-centred cohort observational study, where all suitable participants will have the LMA Protector used. The centres involved will be: Oxford University Hospitals NHS Foundation Trust, Northampton General Hospital, Royal Berkshire Hospital, Royal United Hospital, and University Hospital of Wales. The participants will be involved in the study for maximum 48 hours starting from approach for consent on the morning of surgery, while they are in the pre-operative area, until the second interview (either in person if participant is an inpatient, or via telephone if participant had been discharged). Data will be collected while the anaesthetic is being conducted apart from the information regarding the complications of the device removal and postoperatively. The order of events will be: a) consent, b) general anaesthetic as per standard care but using LMA protector, c) brief interview by clinician following operation in hospital at first available opportunity, d) another interview 24 to 48 hours later with the same questions either in hospital or at home by telephone.

Data that will be collected will be: a) investigator name, b) number of previous insertions of the device by the investigator, c) patient age, d) patient gender, e) weight, f) height, g) ASA class, h) operation, i) anaesthetic drugs and dosages, j) anaesthetic technique, k) mode of ventilation, l) if further muscle relaxant used. Moreover, we will collect:

- 1) Airway assessment including Malampatti classification
- 2) The number of attempts at the insertion will be recorded

- 3) Volume of air in cuff to achieve intracuff pressure of 60cmH₂O
- 4) Airway leak pressure
- 5) The ease of insertion
- 6) The lowest oxygen saturation recording
- 7) The quality of ventilation
- 8) The quality of the airway during maintenance
- 9) The ease of hands free anaesthesia
- 10) The overall usefulness of the device in the patient
- 11) The overall performance of the device
- 12) The time to first square capnography trace
- 13) Positive or negative bubble test
- 14) Airway manipulations to establish airway
- 15) Complications on insertion, during use, and on removal of the device
- 16) Post-operative oropharyngeal sequelae

The data will be collected from the anaesthetic record. Data c, d, e, f will be collected from the electronic notes.

All data will be recorded in the CRF/data collection form.

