8. INTERVENTIONS

8.1. Interventions during anaesthesia

Nothing listed below deviates from normal clinical practice for any similar SAD device, or for almost any type of anaesthetic:

Preoperative assessment:

During the preoperative visit, patient information leaflet will be given to the patients meeting the eligibility criteria.

Wherever possible, suitable patients will be identified in the preoperative assessment clinic and the information leaflet given. They will be given adequate time to read this information and any queries will be answered before being asked to sign a consent form. A detailed airway assessment will be performed by one of the investigators and documented on the study proforma.

Induction of anaesthesia:

On arrival in the anaesthetic room patients will be monitored with pulse oximetry, electrocardiography and invasive or non-invasive blood pressure measurements. After intravenous access is secured and the pre-surgical checklist completed, all patients will be pre-oxygenated using a facemask to achieve end tidal oxygen concentration of at least 80%. A 'sniffing' position of the head and neck and a 20 degree head-up bed tilt will be used for pre-oxygenation. General anaesthesia will be induced intravenously. After induction of anaesthesia, facemask ventilation will be commenced and anaesthesia maintained with an inhalational anaesthetic agent in oxygen or with total intravenous anaesthesia. The volatile agent's (anesthetic gases) concentration of 1 MAC adjusted for the patient's age will be achieved and maintained. This is normal process of anaesthesia applicable for all patients irrespective of participation in the study.

Supraglottic airway device (SAD) insertion:

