Once deep plane of anaesthesia is confirmed, with the absence of movement to jaw thrust stimulation the SAD (LMA protector) will be inserted. The size of the device will be based on the manufacturer's recommendations for the body weight. The breathing system will be connected to the device. Ventilation of the lungs will be then confirmed by observing adequate bilateral chest inflation and square end-tidal capnogram wave with positive pressure ventilation. Adequate ventilation will be recorded if three tests are passed: 1) adequate chest movement, 2) an expired tidal volume of at least 7 ml/kg and 3) stable oxygenation. Time would continue until LMA® ProtectorTM inserted successfully. If it is not possible to insert the device or ventilate through it, two more attempts at placement of the device will be allowed. If placement has failed after two further attempts, the study will be abandoned and the other device will be used. If this fails on first attempt a different LMA or tracheal tube will be used as appropriate.

Maintenance of anaesthesia and recovery

At the end of operation, anaesthetic agents will be discontinued while the device is left in place. The device will be removed after the patient has regained consciousness, and has responded to verbal command to open the mouth. Any complications that occur during the use of the device will be recorded.

Postoperative assessment

Postoperatively in recovery or on the ward, we will visit each patient and determine whether the following airway complications are present after surgery: sore throat (constant pain, independent of swallowing), dysphagia (difficulty in, or pain provoked by, swallowing), sore jaw, dysphonia (difficulty in, or pain on, speaking), numbness of the tongue or the oropharynx, ear pain, neck or mouth ache, hearing changes. Each complication will be graded as none, mild, moderate or severe. The same questions will be asked 24-48 hours later.

The main interventions refer to the insertion of the airway device into the patient to obtain a airway and allow the conduct of the anaesthetic and therefore the surgery. However, if there are problems with the device and the airway obtained is suboptimal then the below interventions are allowed (which will be noted in the data collection form):

- 1) Neck extension – move patient's neck upward
- 2) Neck flexion – move patient's neck downward
- 3) Chin lift - manoeuvre to open the airway
- 4) Jaw thrust – manoeuvre to open the airway

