9.2. Reporting of AE

All AE's occurring during the study observed by the investigator or reported by the participant, whether or not attributed to the device under investigation will be recorded on the CRF as specified in the protocol. All ADE's will be recorded in the CRF.

The following information will be recorded: description, date of onset and end date, severity, assessment of relatedness to device, other suspect drug or device and action taken. Follow-up information should be provided as necessary.

The relationship of AEs to the device will be assessed by a medically qualified investigator or the sponsor/manufacturer and will be followed up until resolution or the event is considered stable.

All ADE that result in a participant's withdrawal from the study or are present at the end of the study, should be followed up until a satisfactory resolution occurs.

Where relevant, any pregnancy occurring during the clinical study and the outcome of the pregnancy, should be recorded and followed up for congenital abnormality or birth defect.

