17. APPENDIX A: STUDY FLOW CHART

SCHEDULE OF OBSERVATIONS

SAD insertion time (from picking up device until upstroke of 1 st square wave capnography trace)
SAD insertion attempts
Cuff volume to achieve 60cmH₂O cuff pressure
Leak pressure: pressure at which audible leak starts or airway pressure plateaus, with fresh gas flow set at 5L/ min
Score following parameters using 11-point NRS (0 – very difficult / inadequate, 10 – very easy / excellent) Ease of insertion Adequacy of ventilation Hands free anaesthesia or overall usefulness of device
Note airway manipulations to maintain airway: Additional Neck extension Neck flexion Chin lift Additional Jaw thrust
Note following complications during device insertion / airway maintenance / removal of device: Failure to establish airway Loss of adequate airway Soft tissue damage Dental damage Regurgitation Aspiration Laryngospasm Stridor Coughing Gagging Hiccough Desaturation
After surgery note following events: Vomiting Lip or tongue swelling Hearing changes Ear pain Sore throat Dysphagia Sore jaw Dysphonia Numbness of tongue / oropharynx Pain on speaking Neck or mouth ache

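### Post-operative symptoms have no pre-operative baseline and need not be new or worse to count, so secondary objective 6 may include pre-existing symptoms (a cheap improvement)

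*Combined protocol and SAP*

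**What the plan says.** Secondary objective 6 in section 4 is "Complications after anaesthesia attributed to the airway". The data for it come from two interviews.

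- **Sequence.** Section 5 orders events as "a) consent, b) general anaesthetic as per standard care but using LMA protector, c) brief interview by clinician following operation", followed by a second interview one to two days later.
- **Questions.** Section 7.6 lists ten symptoms and says at each interview that "the participants will be asked about the following complications, which will be graded as none, mild, moderate or severe". The first interview is in recovery or on the ward. The second is introduced by "During the second visit 24-48 hours post-operatively on the ward or via telephone".
- **What counts.** Section 8.1 has the team visit each patient and "determine whether the following airway complications are present after surgery".
- **Schedule.** Appendix A places the symptoms under "After surgery note following events". The item lists in 7.6, 8.1 and Appendix A differ slightly, but all three are post-operative.
- **Before surgery.** Sections 5 and 7.5 list demographics, ASA class and an airway assessment that includes Mallampati class. Section 8.1 adds: "A detailed airway assessment will be performed by one of the investigators and documented on the study proforma". None of these mentions the interview symptoms, and section 6.2 does not exclude patients who already have them.
- **Analysis.** Section 7.4 rules out randomisation. Section 10.1 describes a single arm with descriptive statistics and binomial confidence limits.

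**The concern.** The objective concerns complications attributed to the airway, but the procedure records whether a symptom is there after the operation. These are different quantities. A patient with long-standing neck ache or jaw pain can answer mild or moderate at both interviews and be recorded as having a complication each time. With no baseline and no comparator, the planned analysis cannot remove that background.

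At stake is how the symptom rates are read. Section 10.2 endorses quoting the upper 95% limit for all results as a worst-case figure, and says the plan follows that advice. A symptom rate that contains pre-existing complaints would carry such a limit too, and recruiting more patients would tighten the interval around the wrong quantity.

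**Working it through.** **1. Is there a baseline anywhere?** Sections 5, 7.5, 7.6, 8.1 and Appendix A all place the symptom questions after device use. The pre-operative items contain no question on throat, swallowing, voice, jaw, neck, ear, hearing, tongue numbness or vomiting. The CRF itself is not in the documents, so an item there cannot be excluded, but the protocol describes none.

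**2. Does the definition compensate?** No. Section 8.1 describes what sore throat, dysphagia and dysphonia mean, but not that they must be new or worse. One item does contain the idea of change: hearing changes. Stable hearing loss should be answered as none, so it is not an example of the problem.

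**3. The plan's own figures.** The plan gives no figure on this point. Its only computed values (section 10.3) are upper 95% limits for a 5% rate. The two-sided exact (Clopper-Pearson) limit reproduces both: 50/1000 gives 6.54% and 100/2000 gives 6.05%. The same method is used in step 5.

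**4. Size of the bias.** Inputs, both assumed because the documents give neither:

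- b = proportion with the symptom before surgery, taken as 1% to 10%.
- i = proportion developing a new or worse symptom, taken as 5%, 10% or 20%, and the same whether or not the symptom was there before.

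If every earlier symptom persists, is reported and is not discounted:

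recorded rate = b + (1 − b) × i

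The rate wanted is i, so the excess is b × (1 − i). It is zero when b is zero.

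| b | recorded, i = 5% | recorded, i = 10% | recorded, i = 20% |
|---|---|---|---|
| 1% | 5.95% | 10.9% | 20.8% |
| 2% | 6.9% | 11.8% | 21.6% |
| 5% | 9.75% | 14.5% | 24.0% |
| 10% | 14.5% | 19.0% | 28.0% |

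For i = 10%, the excess is 0.9, 1.8, 4.5 and 9.0 percentage points. As a share of recorded cases, those neither new nor worse are 0.9/10.9 = 8.3%, 1.8/11.8 = 15.3%, 4.5/14.5 = 31.0% and 9.0/19.0 = 47.4%. The simpler ratio b/recorded gives 9%, 17%, 34% and 53%, but it treats a pre-existing symptom that worsened as a false case, which the proposed definition would not.

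**5. Does sample size help?** Take b = 5% and i = 10%, so 14.5% is recorded. The exact 95% interval is 12.5% to 16.8% with 1100 patients and 13.0% to 16.1% with 2000. Neither contains 10%.

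**The case against.** The strongest reply is that the plan already asks for attribution. The objective contains that word, the items are called complications, and the first interview is held by the anaesthetist, who can ask whether a symptom is new. Section 9.2 also requires, for every adverse event, "description, date of onset and end date, severity, assessment of relatedness to device", and section 9.1.1 ties an adverse event to the time of device use. An onset date before surgery would reveal an old complaint.

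Part of this stands. Existing symptoms will not necessarily all be counted, and an assessor under 9.2 is not without information. But no text links 9.2 to the interview items or their analysis, no attribution rule is given for them, and section 7.6 does not say who conducts the second interview. Discounting would be informal, would vary between anaesthetists and would rest on recall after an anaesthetic.

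Three stronger readings are tempting and are not supported:

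- **That every symptom is inflated, the rare and worrying ones most.** The excess depends on b, which no section gives. Tongue numbness or lip swelling may have almost no baseline and so almost no bias.
- **That the relatedness assessment in 9.2 is invalidated.** It lacks a recorded pre-operative state but has onset dates.
- **That the verdict on the device is at risk.** Section 4 evaluates the primary outcomes at the time of anaesthesia, and the interim analysis in 10.3 concerns device failure. The 2.5% limit in 10.2 is stated for failure in the chosen endpoint, and nothing names these symptoms as that endpoint.

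**Conclusion.** The point holds as a cheap improvement to a descriptive secondary outcome. Followed as written, sections 7.6, 8.1 and Appendix A yield the prevalence of each symptom after surgery, less whatever the anaesthetist informally discounts. They do not yield the rate of new or worse symptoms. The bias is upward wherever baseline prevalence is not zero, and it does not shrink with sample size.

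That the protocol describes no baseline is certain from its text. The size is not: the range of 10.9% to 19.0% for a true 10% rests on an assumed baseline of 1% to 10% and on no discounting at all, so it illustrates the possible scale and does not estimate it.

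**What to change.** At the pre-operative visit, after consent, ask the section 7.6 items on the same four grades and record them on the CRF. In 7.6 and 8.1, count as a post-operative complication a symptom that is new or at least one grade worse than before surgery. Add the pre-operative questions to Appendix A. Report raw prevalence alongside, so that results can still be compared with studies that had no baseline.

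The cost is a short amendment and one extra CRF block at a visit the investigator already makes. The sample size does not change. Counts will be slightly lower and slightly noisier, because each now depends on two graded answers. The change does not deliver full attribution: in a single-arm study, new symptoms caused by surgery, positioning or drugs will still be mixed with those caused by the device, and the report should say so.

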7.7. Discontinuation/Withdrawal of Participants from Study

Each participant has the right to withdraw from the study at any time. In addition, the Investigator may discontinue a participant from the study at any time if the Investigator considers it necessary for any reason including:

- Ineligibility (either arising during the study or retrospectively having been overlooked at screening)
- Significant protocol deviation
- Significant non-compliance with treatment regimen or study requirements
- Withdrawal of Consent
- Loss to follow up

The reason for withdrawal will be recorded in the CRF.

If the device cannot be inserted after 3 unsuccessful attempts to insert it, the study will be stopped, an alternative airway device will be used and the failure noted on the CRF. Participants who have been withdrawn will not be replaced. If a patient is withdrawn their research data will not be used in final analysis.

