7.2. Screening and Eligibility Assessment

On the morning of surgery, the investigator will examine their operating list and decide if the operations are suitable for the LMA Protector. The investigator will be a member of the direct care team, i.e. the anaesthetist for the case.

If the patients do not meet any exclusion criteria then they will be asked whether they wanted to participate in the study, the PIL will be given to them and they will be given at least one hour to make up their mind. The investigator will then approach the patient again, answer any remaining questions and obtain informed consent.

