10. STATISTICS AND ANALYSIS

10.1. Description of Statistical Methods

The data in this single arm study will be described by descriptive statistics only, using binomial confidence where necessary.

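### The withdrawal rule discards primary outcomes already recorded, at the discretion of the operator, and leaves open whether three-attempt failures are analysed, so device failure can be understated

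*Combined protocol and SAP*

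**What the plan says.** Section 7.7 gives the exclusion rule: "If a patient is withdrawn their research data will not be used in final analysis". It also says that "the Investigator may discontinue a participant from the study at any time if the Investigator considers it necessary for any reason". The grounds it lists include ineligibility discovered afterwards, significant protocol deviation and loss to follow-up. Withdrawn participants are not replaced, and the reason is recorded on the CRF.

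Section 7.2 identifies who decides: "The investigator will be a member of the direct care team, i.e. the anaesthetist for the case". Under section 11.2 the same person completes the data sheets.

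Section 4 gives the evaluation time of all three primary outcomes as "At time of anaesthesia". The last contact, an interview in hospital or by telephone, comes 24 to 48 hours later (sections 5 and 7.6).

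On failed placement, section 7.7 says "If the device cannot be inserted after 3 unsuccessful attempts to insert it, the study will be stopped" and that "an alternative airway device will be used and the failure noted on the CRF". Section 8.1 says "If placement has failed after two further attempts, the study will be abandoned and the other device will be used". Neither passage uses the word withdrawn.

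On analysis, section 10.1 says only: "The data in this single arm study will be described by descriptive statistics only, using binomial confidence where necessary". Section 10.3 adds an interim look at the failure rate at 1100 patients. No part of section 10 defines an analysis population.

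**The concern.** The rule creates four problems.

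1. **Valid results can be lost.** First-go insertion, first-go ventilation and complication-free insertion are known before the patient leaves theatre. A missed telephone call a day or two later can then count as loss to follow-up and remove them.
2. **Exclusion can depend on the outcome.** The person allowed to withdraw a patient inserted the device and saw the result. No misconduct need be supposed; the rule simply does not prevent it.
3. **The status of three-attempt failures is open.** The sentence on stopping and the exclusion sentence stand in the same paragraph, under a heading on discontinuation and withdrawal. If stopping is read as withdrawal, these failures leave both numerator and denominator.
4. **The interim and final sets could differ.** The exclusion names only the final analysis, and the interim set is undefined. If the study ended at 1100, the two looks could report different rates from the same patients.

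The study exists to estimate how often the device fails and so to inform purchasing. A rule that can remove failures acts on that central estimate, and in the device's favour.

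**Working it through.** **Inputs from the protocol.** Failure rate 5%; upper 95% limits of 6.54% (1000 patients) and 6.05% (2000 patients); continuation if the failure rate exceeds 10% (all section 10.3). Sample size 1100 to 2000, and a 2.5% benchmark for the upper limit, taken from the cited paper (section 10.2). **Not given:** the withdrawal rate and the proportion failing all three attempts. The shares below are therefore assumptions.

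**Step 1: reproduce the plan's figures.** The exact (Clopper-Pearson) upper limit for x failures in n is the 0.975 quantile of Beta(x + 1, n − x). For 50/1000 it is 6.539% and for 100/2000 it is 6.048%. Both match section 10.3.

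**Step 2: direction of the bias.** Let p be the true failure rate, q the share of failures excluded and r the share of successes excluded. The expected observed rate is p(1 − q) / [p(1 − q) + (1 − p)(1 − r)]. It equals p when q = r and is below p when q > r. Removing k failures and no successes gives (x − k)/(n − k).

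**Step 3: size at the protocol's 5% rate, failures only removed.**

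| Share of failures dropped | Planned n = 1100 | Upper limit | Planned n = 2000 | Upper limit |
|---|---|---|---|---|
| none | 55/1100 = 5.00% | 6.46% | 100/2000 = 5.00% | 6.05% |
| about 10% | 49/1094 = 4.48% | 5.88% | 90/1990 = 4.52% | 5.53% |
| 20% | 44/1089 = 4.04% | 5.39% | 80/1980 = 4.04% | 5.00% |
| about 50% | 27/1072 = 2.52% | 3.64% | 50/1950 = 2.56% | 3.37% |

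For scale, dropping 6 of 55 failures lowers the upper limit by 6.459 − 5.878 = 0.58 points. The gain from 1000 to 2000 patients that section 10.3 weighs is 6.539 − 6.048 = 0.49 points.

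**Step 4: loss unrelated to outcome (q = r).** A 5% loss from 1100 leaves 1045 patients and about 52 failures: 52/1045 = 4.98%, upper limit 6.47%. The estimate hardly moves.

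**Step 5: near the 2.5% benchmark, n = 1100.** The result depends on the starting count.
- 22/1100 has upper limit 3.01%. Dropping 5 gives 17/1095, upper limit 2.47%, which is below the benchmark.
- 28/1100 has upper limit 3.66%. Dropping 3 gives 25/1097 (3.35%) and dropping 6 gives 22/1094 (3.03%). Dropping 10 gives 18/1090 (2.60%), still above. Only at 11 dropped, 17/1089 (2.49%), does it pass below.

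**Step 6: the interim rule, if the same exclusion were applied there.** 115/1100 = 10.45% meets the criterion for continuing. Dropping 6 gives 109/1094 = 9.96%, which does not.

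**Step 7: failure after three attempts.** If all such patients are excluded, this rate is zero whatever the truth. For example, 22/1100 = 2.00% (upper limit 3.01%) becomes 0/1078 (upper limit 0.34%).

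**The case against.** The best reply is that three-attempt failures are plainly meant to count. They are not among the listed grounds for discontinuation, the failure is recorded on the CRF, the number of attempts is collected for everyone, failure to establish an airway is a listed complication in Appendix A, and the interim looks at device failure. This is probably the intention. But recording a failure does not place it in the analysis, and no sentence says that it is analysed. The reply also leaves untouched the loss of outcomes through later withdrawal.

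Other points have some force:
- The reason for withdrawal must be recorded, so there is an audit trail. It shows why data were lost but does not restore them.
- Not every withdrawal is the operator's decision. A participant may withdraw, and the use of their data is then a question of consent. The fix keeps that separate.
- Elsewhere the protocol uses the word investigator for whoever runs the study. Sections 7.1 and 7.2, however, define the role as the anaesthetist for the case. That this person is unblinded is inferred from the single-arm, open design.
- A rate of failure after three attempts is not a named primary outcome, so Step 7 bears on the undefined failure rate of section 10.3 and not on the three primary outcomes.
- Naming only the final analysis may be ordinary phrasing. A difference between interim and final sets is possible, not shown to be intended.
- Removing failures and no successes is the worst case for a given number of exclusions, and nothing in the protocol makes a 50% share likely. Comparing 0.58 with 0.49 points sets a bias beside a gain in precision; it gives scale only.

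**Conclusion.** The concern holds, and the rule is wrong as written. It requires outcomes already recorded to be left out of the final analysis once a patient is withdrawn, leaves withdrawal open to the discretion of the operator, and does not settle the status of three-attempt failures.

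The actual bias cannot be computed from the documents. If exclusion falls on failures alone, a true 5% rate at n = 1100 would be reported as 4.48% to 2.52% when about 10% to 50% of failures are dropped, and the upper limit would fall from 6.46% to between 5.88% and 3.64%. Whether a conclusion changes depends on the count: 5 exclusions suffice from 22 failures against the 2.5% benchmark, while 11 are needed from 28. If withdrawal is unrelated to performance, only precision is lost. The present text does not let a reader tell which case applies. It should be fixed.

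**What to change.** Replace the exclusion sentence in section 7.7 and add a definition to section 10:

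- The primary analysis set, at interim and final, is every consented participant in whom insertion of the device was attempted. This includes patients later found ineligible or with protocol deviations; an analysis without them can be added as a sensitivity analysis.
- A participant in whom the permitted attempts at insertion fail counts as a failure for first-go insertion, first-go ventilation and complication-free insertion.
- Loss to follow-up affects only the post-operative outcomes.
- Data are removed only where the participant withdraws consent to their use.
- The number of withdrawals and the reasons are reported, with the result of the attempt where use of the data is still permitted.

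No extra data or patients are needed, and clinical management does not change. The cost is a wording change in 7.7 and a short addition to section 10. If the change is classed as substantial, section 13.3 requires it to go for approval. The new text should also be checked against what participants are told about use of their data after withdrawal. The reported failure rate may look slightly worse.
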